## **15) Withdrawal of subjects**

If significant psychopathology or other disqualifying condition is discovered during the psychiatric assessment or if it becomes evident that the participant is unable or unwilling to comply with study procedures, research study staff may withdraw that individual from the study.

Subjects can voluntarily withdraw from the study at any time by speaking with the PI or study team. The study will then ensure the subject withdraws from the study safely and will provide any necessary follow-up care.

In order to protect subjects, study resources and the integrity of study data, the Principal Investigator reserves the right to remove any subject at his discretion from the study. This will be communicated to prospective subjects during the consent process.

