## 2) Lay Summary (approximately 400 words)

### **Main Study Arm:**

[name] and colleagues are conducting a research study funded by the Department of Defense to understand the effectiveness of a six-week course of light exposure on cognitive functioning, mood, activity, and sleep in people that have suffered a mild traumatic brain injury (mTBI) or “concussion.” This study will consist of four visits to the University of Arizona.

During the course of the study, participants will complete two cognitive testing sessions and magnetic resonance imaging (MRI) scans (1 hour each), which will occur 6 weeks apart. During the intervening 6-week period, participants will use a commercially available light device to provide 30-minutes of light exposure each morning. During the two testing and MRI scan sessions, participants will undergo a series of tests of attention, concentration, memory, and other cognitive abilities, and will complete clinical measures to assess mood and post-concussion symptom severity. Daily activity and sleep patterns during the entire 13-week period will also be monitored using self-report diaries, questionnaires, and a wrist worn activity monitor. This monitoring will continue for an additional 6 weeks after termination of the light exposure for subjects who elect to participate in this optional research.

In this study, we will use functional and structural brain imaging techniques such as functional magnetic resonance imaging (fMRI) and diffusion tensor imaging (DTI) to evaluate brain function and brain structure before and after the 6-week light exposure period. Identifying and mapping the brain systems before and after light exposure may help researchers develop further insights into the relationship between concussion, light exposure, sleep, and brain function.

Those deemed eligible to take part in this study will have experienced a mild traumatic brain injury (mTBI) or concussion during the past 18 months, but no sooner than four weeks prior to the screening. Approximately 40 individuals between the ages of 18 and 50 will participate in this study in order to obtain a final dataset of 30 due to attrition.

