#### **5) Study Population**

##### **Main Study Arm:**

**FORM: Application for Human Research**

NUMBER	FORM DATE	PAGE
F200	02/2014	14 of 39

Forty (40) individuals between the ages of 18 and 50 with a documented history of a “concussion” or mTBI in the preceding 18 months but no sooner than 4 weeks prior to the screening will be recruited to participate in the main study arm. It is anticipated that approximately 6 participants (i.e., 17%) will withdraw early or fail to comply with procedures. Thus, a total of 40 participants will be run to achieve a total sample size of 30 complete datasets. The occurrence of a concussion or mTBI must be documented by a medical/objective professional (e.g., sports trainer, coach, physician, nurse, etc.) report. In addition, at least half of the participants recruited for each condition will be required to have complaints consistent with sleep onset insomnia (i.e., trouble falling asleep) as measured by Insomnia Severity Index (ISI) or delayed sleep phase disorder (i.e., not feeling sleepy at bedtime and/or not able to fall asleep until much later than bedtime). Participants with a lifetime history of head injury leading to loss of consciousness greater than 30 minutes will be excluded. Other exclusion criteria will include any current medical condition that would be contraindicated for scanning, other known neuropathology (e.g., tumor, neurodegenerative disease, normal pressure hydrocephalus, etc.), abnormal visual acuity that is not corrected by contact lenses, metal within the body, or time since injury exceeding 18 months.

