### Initial Assessment

Upon arrival, all participants will have the procedures thoroughly explained and will complete verbal and written informed consent procedures. Participants will complete the Mini-International Neuropsychiatric Interview (MINI), the Screen Time Questionnaire, Personality Assessment Inventory (PAI), the Wechsler Abbreviated Scale of Intelligence II (WASITM II) as a measure of

**FORM:** Application for Human Research

NUMBER	FORM DATE	PAGE
F200	02/2014	20 of 39

intelligence and the VA National Traumatic Brain Injury Neurobehavioral Symptom Inventory (NSI). The first visit is still considered part of the initial screening portion of the study and the subject's responses to the assessments and questionnaires will be evaluated to determine his or her eligibility for subsequent portions of the study. For example, if significant psychopathology or other disqualifying condition is discovered during the psychiatric assessment or if it becomes evident that the participant is unable or unwilling to comply with study procedures, research study staff may withdraw that individual from the study. If the participant is deemed ineligible for continuation, compensation will be provided for the time he or she participated according to a prorated schedule. At the conclusion of the initial assessment, eligible participants will be fitted with a wrist actigraph (Actiwatch AW-Spectrum) for measuring sleep-wake patterns and trained in its use. In addition, participants will be given a sleep diary to be completed upon awakening each morning. Subjects will wear the wrist actigraph and complete sleep diaries and scales for the week prior to their baseline assessment/scanning session.

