whether to use the light immediately upon arising, or after morning hygiene, meals, drive, etc., but will still ensure that all treatment occur in the morning hours. The instrument is equipped with a timer to ensure 30 minutes of exposure. Appropriate use will involve placing the light device at a distance between 12-24 inches, offset from center to reduce glare. Participants will be instructed not to look directly at the light source, but to allow the light to enter from their peripheral vision. Each morning, within 2 hours of arising from sleep, participants will 1) document the time, indicate sleepiness using the Stanford Sleepiness Scale (SSS), activate the light device, and document the sleep and wake times from the previous day. At the completion of the light period, participants will again indicate sleepiness using the SSS. To further monitor compliance, the wrist actigraph will also include a light monitor. Participants will be instructed to ensure that the light sensor of the actigraph is exposed to the light source for the full 30-minute duration in order to verify compliance. This will permit cross-verification that subjects have in fact used the blue wavelength light at the specified times (and will allow co-variation for additional light effects in statistical analyses). MBLT exposure will be conducted daily for 6-weeks for all participants. Participants will also be contacted weekly by phone to ensure compliance, answer questions, and collect a weekly Epworth Sleepiness Scale.

Half of the participants will be randomly assigned to the morning MBLT or a sham placebo light treatment (SPLT). Participants in the MBLT group will be administered blue light therapy using the standard goLITE BLU device, whereas participants in the SPLT group will be given identical appearing goLITE devices where the standard bright blue-wavelength LEDs have been replaced with amber LEDs. The goLITE BLU has been shown to have a narrow bandwidth, peaking at  $\lambda = 469$  nm, at 214 Lux, and panel irradiance  $\text{mW/cm}^2 = 1.23$  at 20 cm. A similar appearing amber LED system (goLITE AMBER) will be employed for the SPLT devices, but will peak at  $\lambda = 566$  nm, at 180 Lux, and total irradiance  $(\text{mW/cm}^2) = 0.58$ .

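### Participants can be removed after randomisation at discretion, the target is complete datasets, and no as-randomised analysis is specified, so the plan allows a completer or complier comparison of blue with amber light

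*Combined protocol and SAP*

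**What the plan says.** Section 15 (Withdrawal of subjects) gives two powers of removal. If a participant proves "unable or unwilling to comply with study procedures, research study staff may withdraw that individual from the study". Separately, "the Principal Investigator reserves the right to remove any subject at his discretion from the study"; the grounds given are protection of subjects, of resources and of data integrity. Neither power has criteria or a time limit, and the section does not require the decision to be made blind to arm.

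Section 5 (Study Population, Main Study Arm) expects that "approximately 6 participants (i.e., 17%) will withdraw early or fail to comply with procedures", and continues: "Thus, a total of 40 participants will be run to achieve a total sample size of 30 complete datasets". The Lay Summary describes about 40 participants "in order to obtain a final dataset of 30 due to attrition".

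The section headed Biostatistical Analysis interprets four possible outcomes of the comparison of morning blue light therapy (MBLT) with sham amber light (SPLT). It does not say who is analysed, whether participants stay in their assigned arm, how missing post-treatment scores are handled, or whether outcomes are collected after removal.

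Two other places bear on the point. Under Initial Assessment in Section 7, the same non-compliance wording appears as a screening step: "The first visit is still considered part of the initial screening portion of the study". Section 12 (Subject compensation) pays $900 for completing the third visit and returning the equipment, and $1,000 if there is also evidence that the at-home procedures were followed.

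**The concern.** The conclusion that MBLT helps relative to placebo rests on the randomised contrast. That contrast is protected only if the people compared are those allocated, whatever they did afterwards. Adherence to a daily light can depend on its colour and on how the participant is faring. If participants doing badly in one arm stop using the device and are then removed, that arm's mean improves for a reason unrelated to treatment.

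Three features of the plan make this more than a formality.

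- No compliance threshold is stated, and the daily time limit differs: 10:30 a.m. in the opening text of Section 7, noon under Six-Week Light Exposure Treatment. The same participant could be judged compliant or not, so these passages need to be reconciled.
- Compliance is verified partly with an actigraph that records red, green and blue light, so the evidence could reveal the arm. The documents do not say that the person judging compliance is blind.
- The actigraph data are downloaded after week 7, about when post-treatment outcomes are collected. A decision on compliance could therefore be made with outcomes available.

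**Working it through.** **1. The plan's own figures.** Inputs from Section 5: 30 complete datasets, about 6 losses stated as 17%, 40 run.

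- Inflating for 17% loss: 30 / (1 − 0.17) = 36.1, so 37 rather than 40.
- Subtracting: 40 − 6 = 34 rather than 30.
- 6/40 = 15%; 6/35 = 17.1%; 6/36 = 16.7%.
- Going from 40 to 30 is a loss of 10/40 = 25%.

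The figure of 40 is not reproduced from the stated loss. The planned shortfall (10) exceeds the expected loss (6), and the plan does not say how either number divides between losses before and after randomisation.

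**2. What happens to a randomised participant who does not use the light.** Section 15 lets staff withdraw them. Section 5 counts them as a loss. The Lay Summary calls the remaining 30 the final dataset. The biostatistical section does not bring them back. Section 12 shows that they may instead finish the third visit. Both routes are open, and nothing fixes the choice in advance.

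**3. Size of the bias, by assumption.** The documents give no SD, significance level, power or removal rate by arm. Suppose a fraction f of one arm is removed and those removed average m SD worse than those kept. The mean of everyone in that arm is (kept mean) − f × m, so analysing only those kept shifts the arm by f × m in its favour. Any removal in the other arm is taken to be unrelated to outcome. With no true effect, the rejection rate of a nominal two-sided 5% t-test follows from the noncentral t distribution with noncentrality (f × m)/SE.

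If both arms end at 15, SE = √(2/15) = 0.365 SD. If removal occurs in one arm of 20 only, 25% removal leaves 15 v 20, SE = √(1/15 + 1/20) = 0.34 SD, and 15% removal leaves 17 v 20, SE = √(1/17 + 1/20) = 0.33 SD.

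| f | m | Bias f × m | Error rate, 15 v 15 | Error rate, removal in one arm only |
|---|---|---|---|---|
| 0.15 | 0.5 | 0.075 SD | 5.5% | 5.6% (17 v 20) |
| 0.15 | 1.0 | 0.15 SD | 6.8% | 7.3% (17 v 20) |
| 0.25 | 0.5 | 0.125 SD | 6.3% | 6.5% (15 v 20) |
| 0.25 | 1.0 | 0.25 SD | 10.1% | 11.0% (15 v 20) |

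If removal is unrelated to outcome, or acts alike in both arms, the bias is zero and the error rate stays at 5%.

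**4. Precision.** Under an assumed two-sided 5% level and 80% power, the detectable difference is 1.06 SD with 15 per arm and 0.91 SD with 20 per arm. The second figure is a best case: it needs all 40 to be randomised and to have outcome data.

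**The case against.** The strongest reply is that the plan permits removal from the study but nowhere says that the data of those removed are discarded. The figure of 30 can be read as a recruitment target that allows for attrition, not as a definition of the analysis set. The non-compliance sentence also appears word for word as a screening rule at the first visit, before any light is issued, where it does no harm. The payment schedule expects some poor compliers to reach the third visit and pays them $900 for it. Investigator-discretion clauses are common and serve safety.

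Much of this stands. A reader might infer that the arms compared will not be the arms randomised. The documents do not support that: they leave the possibility open without prescribing it. A reader might also infer that a quarter of the randomised participants will be excluded. The 25% is the planned gap between participants run and datasets wanted. It may include people lost at the first visit or during baseline, before a device was issued, and the plan itself expects about 6 losses of all kinds. Nor do the documents say that those deciding on removal will know the arm; they only fail to say that they will not.

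The reply does not close the gap. Section 15 repeats the screening sentence without its screening limit and adds a wider power over any subject. Section 5 counts failure to comply as a loss. The analysis section is silent, so the choice between keeping and dropping these participants could be made after the data are seen.

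**Conclusion.** The concern holds in a limited form. Post-randomisation removal is open-ended, non-compliers are counted as losses toward a final dataset of 30, and no as-randomised analysis is specified. A completer or complier comparison of MBLT with SPLT would therefore be consistent with the plan as written.

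The bias cannot be derived from the documents and ranges from zero upward. The range of 0.075 to 0.25 SD, with a two-sided error of 5.5% to about 11% in place of 5%, rests on assumed removal fractions and outcome gaps, with selective removal in one arm only. It illustrates what is at stake and is not a prediction. Against a standard error of 0.33 to 0.37 SD, the top of that range is material and the bottom is small. The point should be corrected before analysis, but it does not show that the randomised comparison has been lost.

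**What to change.** - **Removal.** State in Section 15 that, after randomisation, neither non-compliance nor investigator discretion removes a participant from outcome collection or from the analysis. This concerns data only and leaves decisions about the light itself to the clinical sections. Screening removals under Initial Assessment can stay as they are.
- **Follow-up.** Invite participants who stop the light, or are withdrawn from it, to the 6-week visit where consent and safety allow.
- **Decision and reporting.** Have any removal decided blind to arm where possible. Report reasons and numbers by arm, separating losses before and after randomisation.
- **Primary analysis.** In the biostatistical section, define the MBLT v SPLT comparison as all randomised participants in their assigned arm, using a mixed model or multiple imputation for missing post-treatment scores. Give compliers and completers as a supporting analysis, with compliance defined in advance.
- **Consistency.** Reconcile 40, 6, 17% and 30 in Section 5, and the two daily time limits in Section 7.

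The cost is mostly wording. A few poor compliers attend a visit already in the schedule, for which a payment tier exists, although Section 12 caps payment at $275 for those who discontinue during the light period. The estimated effect may be somewhat smaller than in a complier analysis.

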**FORM: Application for Human Research**

NUMBER	FORM DATE	PAGE
F200	02/2014	37 of 39

**16) Sharing of results with subjects**

Subjects will be informed of any new information that pertains to their rights or safety immediately.

Subjects have the right to see and get a copy of their health information that is used or shared for treatment or for payment. To ask for this information, subjects will contact the person in charge of this research study. Subjects may only get such information after the research is finished.

**SECTION 4: LIST OF ATTACHMENTS FOR THIS SUBMISSION**

Document Name	Version Date
1. F107	1. 06/16/15
2. Protocol	2. 04/14/14
3. Bright Light Treatment Protocol Schema	3. N/A
4. Informed Consent & PHI Form	4. 06/16/15
5. Payment Form	5. 04/08/14
6. Phone Screening Form	6. 06/16/15
7. Phone Script	7. 06/16/15
8. UAMC SRA Approval Letter	8. 04/03/14
9. Grant Application	9. AWAITING
10. Notice of Recommendation for Funding	10. 11/22/13
11. PI CV	11. 04/04/14
12. goLITE Blu Pamphlet	12. 2013
13. Screen Time	13. N/A
14. Day of Scan Info Questionnaire	14. 05/21/13
15. Second Day of Scan Questionnaire	15. 05/21/13
16. Sleep Diary	16. N/A
17. Watch & Light Subject Guide	17. N/A
18. Print Ad	18. 06/10/15
19. Flyer Ad	19. 06/10/15
20. Radio Ad	20. 06/10/15
21. Questionnaire Task List	21. 04/02/14
22. ANAM4 Scale	22. March 2007
23. BART	23. N/A
24. BDI-II	24. N/A
25. EVAR	25. N/A
26. FOSQ	26. N/A
27. GNG	27. N/A
28. IBI	28. N/A
29. MEQ	29. N/A
30. MINI 6.0	30. 01/01/09
31. MSIT	31. N/A

**FORM: Application for Human Research**

NUMBER	FORM DATE	PAGE
F200	02/2014	38 of 39

32. N-Back	32. N/A
33. NSI	33. N/A
34. PAI	34. N/A
35. PHQ-9	35. 1999
36. PSG	36. N/A
37. PSQ1	37. 1989
38. PVT	38. N/A
39. RBANS	39. 1998
40. Rivermead Questionnaire	40. 2006
41. STAI	41. N/A
42. SSS	42. N/A
43. TOL	43. N/A
44. WASI	44. 2011
45. Medical Monitor CV ([name])	45. 2013
46. FITBIR Data Sharing Policy	46. 03/27/14
47. Instructions for using light device	47. 06/16/15
48. Flyer – BL2 General	48. 06/16/15
49. Flyer- BL2 mTBI Short Flyer	49. 06/16/15

## Submission List for F200: Application for Human Research

**Required items for all F200 submissions:**

- F107: Verification of Training Form
- Current PI/Co-PI CVs or biosketch, if not included with copy of grant application

**Other Items as applicable:**

- **Data Collection Tools** – surveys, questionnaires, diaries not included in the protocol, data abstraction form for records review
- **Grant Application(s)** – complete copy of grant, regardless of home institution or funding agency, and a copy of the Notice of Grant Award
- **Informed Consent/Permission/Accent Form(s)** – including study specific release of information documents, DHHS approved sample consent forms. If consent will not be documented in writing, a script of information to be provided orally to subjects
- Other Approval letters (e.g., school districts, Tribal, other IRB approvals)
- **Participant Materials** – All written materials to be provided to or meant to be seen or heard by subjects (e.g. study newsletter, physician to participant letter, wallet cards, incentive items, holiday/birthday cards, certificates, instructional videos/written guides, calendars, certification of achievement, etc.)
- **PHI Authorization Form(s)**
- **Protocol** – including all amendments/revisions, sub- or extension-studies

**FORM: Application for Human Research**

NUMBER	FORM DATE	PAGE
F200	02/2014	39 of 39

- **Radiation Safety Review** letter
- **Recruitment Materials** – telephone scripts, flyers, brochures, websites, email texts, radio/television spots, newspaper advertisements, press releases, etc.
- **Site Authorizations** for research purposes and/or access to administrative records/samples
  - UAHN University Campus, South Campus and clinics Site Review Authority (SRA) approval

**Submitting documents to the IRB**

All materials must be typed and submitted electronically. Maintain electronic copies of all information submitted to the HSPP office in case revisions are required. It is recommended that version dates be used while naming documents.

1. Documents must be submitted to the [[contact]](mailto:[contact]) account and not to individual staff email accounts. After contact by a staff member future correspondence may be communicated directly to the staff member concerning the submission.
2. **If acknowledgement of receipt is needed, please request a "Read Receipt" through your email server.** If you use Microsoft Outlook 2007, this is accomplished by clicking "Options" and choosing the "Request a Read Receipt" checkbox in a new email.
3. One submission request per email (e.g. one new project submission, one continuing review plus attachments, or one modification request).
4. All submissions must have signatures. An email acknowledgement in place of a signature will not be acceptable. If electronic signatures are not available for use, the signature pages may be signed and scanned as a separate Adobe PDF document and attached to the submission email.
5. **Microsoft Word documents are REQUIRED** for (applications, consents, recruitment materials, and data collection instruments (if available). PDFs may be submitted for documents that typically are not revised by the IRB (e.g. Investigator Brochures, sponsor protocols).
6. The email subject line must include: IRB # (if assigned one), PI Last Name, and type of submission (Modification, New Project, Continuing Review, Reportable Item, etc.).
7. The email must provide a list of the documents submitted for review. While the documents attached do not have to adhere to a specific naming scheme, it is requested that each document be named to clearly reflect what is inside.

**Submissions not following these guidelines will be returned without review**
